7.2. Data display (feeder study and previous treatment) descriptors

The feeder study and previous treatment group (immediately prior to entering the extension study DIUR-006) descriptors to be used in outputs are listed in

Table 1 below. The full data display descriptor is preferred, although the abbreviated option in the third column may be used if there is not enough space on the page.

Table 1: Feeder study and previous treatment descriptors

Feeder study/previous treatment	Full data display descriptor	Abbreviated data display descriptor
	Feeder study	
DIUR-003	DIUR-003	DIUR-003
DIUR-005	DIUR-005	DIUR-005
Chronocort® with previou	us treatment (immediately prior to baseli	ne visit)

Chronocort® (subjects entering immediately from DIUR-005 Chronocort® arm)	Chronocort	Cct
Chronocort® with Standard glucocorticoid replacement therapy (subjects entering immediately from DIUR-005 Standard GC arm)	Standard GC therapy	SGC
Chronocort® with non-study glucocorticoid replacement therapy (subjects from DIUR-003 and DIUR-005 gap subject)*	Non-Study GC therapy	NGC

^{*}Note: For subjects from study DIUR-005 who had a gap between completing study DIUR-005 and starting study DIUR-006 and subjects from study DIUR-003, non-study GC therapy immediately prior to entering DIUR-006 will be per local clinical practice.

8. General considerations for data analyses

All statistical analyses will be performed using the software package SAS® version 9.2 or higher.

8.1. Standard summary statistics

The standard summary statistics for continuous baseline and outcome variables are: N, mean, standard deviation (SD), median, quartiles, minimum and maximum. The standard summary statistics for categorical baseline and outcome variables are: count and proportion (expressed as percentage). Geometric mean and coefficient of variation will also be presented for variables which will subsequently be log-transformed during the analysis.

8.2. Statistical significance and multiple testing strategy

Since all subjects participating in this trial will be receiving Chronocort®, there will be no formal treatment comparisons. Summaries over time will be produced for safety and efficacy parameters.

9.1. Missing data

Blood samples for analysis of 17-OHP and A4 values are to be taken at the baseline, Week 4, Week 12, Week 24 and 6-monthly visits at both 09:00 and 13:00 hours, with a window of +/- one hour allowed. Missing 17-OHP and A4 values will not be imputed. In calculating the mean of the 09:00 and 13:00 SDS, if one value is missing, then only the non-missing value will be used. If both values are missing, the mean value will be missing.

For subjects based in the US receiving domiciliary visits, only one blood sample for analysis of 17-OHP and A4 will be taken, at either 09:00 or 13:00 hours.

When calculations must be based upon incomplete dates the following process will be used. If year is missing do not impute. The value should be considered missing. If year is populated but both month and day are missing then the date defaults to 1st July. If day only is missing then the day defaults to the 15th of the month.

For adverse events and concomitant medications, the following date imputation methods will be used:

Partial start date

- If the day part is missing then impute as the latest of [1st of the month, date of first dose of Chronocort^{®1}].
- if the month part is missing then impute as the latest of [1st of January, date of first dose of Chronocort^{®1}].
- if the year is missing then do not impute.

Partial end date

- if the day part is missing then impute as the earliest of [last date applicable to the respective month part, date of last study contact or interim data cut-off date].
- If the month part is missing then impute as the earliest of [31st of December, date of last study contact or interim data cut-off date].
- If year part is missing then do not impute.

For definition of treatment emergent and ongoing, if partial dates are only available for start and end, then we are conservative and assume treatment emergent/ongoing.

9.2. Derived and transformed data

9.2.1. Baseline and demographic derivations

The age of the subject in years will be determined using the date of birth (recorded at screening) and the date of consent. Since year only is being collected for this study, age in whole years will be calculated as:

• Year of consent into study DIUR-006 - year of birth.

¹ Consider first dose date of Chronocort® unless can be unequivocally determined that the event did not occur on or after the first dose of Chronocort®, based on available information for the partial date.

Statistical Analysis Plan

Version: 6.0 12 July 2022

Time since CAH diagnosis will be determined using the date of CAH diagnosis captured in the electronic case record form eCRF and will be calculated as:

Date of DIUR-006 baseline visit - date of CAH diagnosis + 1.

The derivation of time since CAH diagnosis partial dates will be handled as described in Section 9.1

Body surface area (m²) will be calculated using the Dubois formula,

Weight
$$(kg)^{0.425} \times Height (cm)^{0.725} \times 0.007184$$
.

9.2.2. Derivations of SDS scores

As part of the secondary objectives, the change from pre-Chronocort® baseline (see Section 9.3.2) in SDS of 17-OHP and A4 will be calculated. The SDS is defined as the absolute (unsigned) number of standard deviations above or below the average of the lower and upper limit of normal.

For each of the 17-OHP and A4 concentrations at each visit at each time point (09:00, 13:00), the natural logarithm will be taken and the SDS will be calculated by counting the number of standard deviations which are above or below the mean of the log transformed range (given in Table 3). The mean of the SDS scores for each androgen will be calculated over the two timepoints. Missing values will be handled as described in Section 9.1.

Table 2: Normal reference ranges for 17-OHP and A4

	Male	Female
17-OHP	1.2* – 6.7 nmol/L	1.2* – 8.6 nmol/L
A4	1.4 – 5.2 nmol/L	1.0 – 7 nmol/L

Source: Mayo Clinic.

17-OHP: http://www.mayomedicallaboratories.com/test-catalog/Clinical+and+Interpretive/9231.

Please note the upper reference range for females is during the luteal phase.

Table 8) will be used in the derivation of the average SDS score. This will enable calculation of an 'unsigned' SDS score which can be used to assess potential overtreatment as well as undertreatment.

A4: http://www.mayomedicallaboratories.com/test-catalog/Clinical+and+Interpretive/9709

^{*}There is no lower reference range available for 17-OHP, hence the lower limit of the optimal range (provided in

Statistical Analysis Plan

Version: 6.0 12 July 2022

Table 3: Mean and SD of normal log-transformed range

Analyte	Sex	mean of log _e -transformed range [log _e (nmol/L)]	SD of log _e -transformed range [log _e (nmol/L)]
17-OHP	Male	1.042	0.430
	Female	1.167	0.492
A4	Male	0.993	0.328
	Female	0.973	0.486

Source: Mayo Clinic.

17-OHP: http://www.mayomedicallaboratories.com/test-catalog/Clinical+and+Interpretive/9231.

Please note the upper reference range for females is during the luteal phase.

A4: http://www.mayomedicallaboratories.com/test-catalog/Clinical+and+Interpretive/9709

The mean of the "normal" log-transformed range was calculated by averaging the natural logarithm of the upper and lower limit given in Table 2. The SD of the log-transformed range was approximated by dividing the range of the log-transformed values by four.

9.2.3. Conversion factors

For the conversion of standard glucocorticoid replacement therapy to hydrocortisone, the conversion factors (Finkielstain 2012) are given in Table 4.

Table 4: Conversion factors for standard glucocorticoid replacement therapy to hydrocortisone

Standard glucocorticoid replacement therapy	Conversion factor
Prednisone or prednisolone	5
Dexamethasone*	80

Note: The conversion factor for Chronocort® is 1.

For example, if a subject was previously taking 6mg of prednisone daily, this would be multiplied by a conversion factor of five and the equivalent hydrocortisone daily dose would be 30mg.

If a subject was previously taking prednisone in combination with hydrocortisone, then a conversion factor of five would be applied to the prednisone component of the dose, and a conversion factor of one would be applied to the hydrocortisone component of the dose, and the two added together.

All laboratory results will be reported using the International System (SI) of units and conventional units. If for any reason the results are not collected in SI units, a conversion to SI units will be performed. Examples of some conversions to SI units are given in Table 5.

^{*} up to a maximum starting dose of Chronocort® 30mg, split as 20mg at night 10mg in the morning

Version: 6.0 12 July 2022

Table 5: SI unit conversions

Quantity	Conversion to SI units		
17-OHP	1 ng/dL	= 0.0303	nmol/L
ACTH	1 pg/mL	= 0.22	pmol/L
Androstenedione	1 ng/dL	= 0.0349	nmol/L
Glucose	1 mg/dL	= 0.0555	mmol/L
Insulin	1 μIU/mL	= 6.945	pmol/L
Osteocalcin	1 μg/L	= 0.171	nmol/L

9.2.4. Derivation of reference flag for DEXA scan results

A reference flag will be derived for DEXA scan results, which will be assigning Low, Normal or High values to the measurements according to Table 6.

Table 6: Normal reference ranges of DEXA scan results

Parameter	Normal range (unit)
Total fat mass	6.3 to 50 kg
Total lean mass	29 to 63.5 kg
Total bone mineral density	0.9 to 1.3 g/cm2
T score	-1 to +2
Z score	-1.5 to +2

9.2.5. Coding of adverse events, concomitant medications, etc.

Adverse events (AEs) and medical history will be coded using the Medical Dictionary for Regulatory Activities (MedDRA) version 19.0 or later (the exact version to be determined when coding is done). Coding will be to the level of the lowest level term (LLT). Concomitant medications and pretreatment CAH medications will be coded using the World Health Organisation (WHO) Drug Dictionary including Anatomical Therapeutic Chemical (ATC) drug classification.

9.3. **Assessment time windows**

9.3.1. Definition of permissible time windows

Actual study day will be calculated by:

• Date of assessment - Date of first dose + 1 (or Date of assessment - Date of first dose if the assessment is before the date of first dose).

Version: 6.0

Protocol No.: DIUR-006

However, due to the first dose being scheduled at 23:00h on the evening of the baseline assessment¹ (Visit 1), a window of +4 hours will be used so that if the time of first dose falls within the window,

the date of first dose will be considered to be the planned date of first dose. For example, if a subject takes their first dose at 01:00h the day after the baseline assessment, the date used for the calculation of study day will still be the day of the baseline assessment.

Vital signs, laboratory data, bone turnover markers, physical examinations (including weight, BMI and waist circumference), endocrine profile (17-OHP and A4), signs and symptoms of adrenal insufficiency, DEXA scans and QoL data will be summarised according to scheduled visit.

Please note that visits 2 and 3 are when specific assessments of 17-OHP, A4 and signs and symptoms of adrenal insufficiency are performed. Any extreme deviations between the actual study day of the scheduled visit and the target study day (see Table 7) will be discussed at the Data Review Meeting. A deviation will be considered extreme if more than +/- 3 weeks (+/- 21 days) from visit 2, +/- 4 weeks (+/- 28 days) from visit 3 and 4, or +/- 3 months (+/- 84 days) for visit 5 and onwards. If 2 or more visits (including unscheduled visits) occur within the same analysis window, then the visit closest to the target study day will be used in the descriptive summaries. In case of equidistant visits to the target study day, then the earliest visit will be used in the analyses. All visits will be displayed in the listings.

Table 7: Target study day for visit assessments

Visit number	Visit description	Target study day	Target study day range
Visit 0	Visit 0/Screening	-14 to -1	
Visit 1	Visit 1/Baseline	1	
Visit 2	Visit 2/Week 4	29	8-50
Visit 3	Visit 3/Week 12	85	57-113
Visit 4	Visit 4/Week 24	169	141-197
6-monthly visits from visit 5 onwards			
Visit 5	Visit 5/Month 12	365	281-449
Visit 6	Visit 6/Month 18	548	464-632
Visit 7	Visit 7/Month 24	730	646-814
Visit 8	Visit 8/Month 30	913	829-997
Visit 9	Visit 9/Month 36	1095	1011-1179

¹ For subjects entering immediately from the DIUR-005 feeder study this will be the evening of the second day of Visit 4 (Week 24) of the DIUR-005 study.

Protocol No.: DIUR-006

Visit 10	Visit 10/Month 42	1278	1194-1362
Visit 11	Visit 11/Month 48	1460	1376-1544
Visit 12	Visit 12/Month 54	1643	1559-1727
Visit 13	Visit 13/Month 60	1825	1741-1909
Visit 14	Visit 14/Month 66	2008	1924-2092
End of Study/Early Discontinuation	End of Study	Last non-missing assessment within 48 hours of last dose of Chronocort®	

Note: There is no study day 0 as per CDISC standards. Study day 1 is first day of dosing.

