Once the baseline assessments are completed, the subjects will be given sufficient Chronocort® to use until the next visit at Week 4. Subjects entering immediately from study DIUR-005 who were previously on Chronocort® will continue on the same dose of Chronocort® as they were receiving at the end of the feeder study. Subjects from study DIUR-005 on standard therapy, subjects from DIUR-005 who had a gap between completing study DIUR-005 and starting study DIUR-006 during which they received standard glucocorticoid therapy, and subjects from study DIUR-003 will have their initial dose of Chronocort® determined using the hydrocortisone equivalent of their previous treatment (immediately prior to the baseline visit).

All subjects will return to the study centre at 4, 12 and 24 weeks after starting study DIUR-006 for additional blood tests and dose titration, if necessary. Visits thereafter will take place at 6-monthly intervals. If there is a change of dose, a dose titration interim visit or telephone call will be needed in between the 6-monthly visits.

Version: 20.0 – 16 Jun 2022 Page **23** of **96** 

All subjects will receive welfare telephone calls at 3 monthly intervals, and unscheduled visits will be arranged if necessary. Subjects will be provided with Chronocort® supplies from the study pharmacy at either 3- or 6-monthly intervals.

At the end of the study subjects will have the option to enter a second long-term study (DIUR-015) to enable them to continue to receive open-label Chronocort® until it is commercially available in their region or it is decided to stop Chronocort® treatment. Subjects who decide to enter the DIUR-015 study immediately following this DIUR-006 study do not require a telephone call 30 days after the end of this study. If there is a gap between finishing this DIUR-006 study and entering the DIUR-015 study of greater than 30 days, then the 30-day telephone call is required.

All subjects have the following assessments conducted during the study (see Table 1):

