### 11.1 Visit Schedule

A window of +/- 3 days is allowed around each visit up to and including the Week 18 visit. After Week 18, a visit window of +/- 2 weeks is allowed around each visit. If a visit is delayed e.g. due to sick day rules, the visit schedule will continue as scheduled i.e. the original timings will not be adjusted based on the delayed visit date.

If a participant has received the COVID-19 vaccine then the next visit must be scheduled at least 5 days post-vaccine.

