### 11.1.7 Week 24 and then every 6-months (± 2 Weeks)

Subjects will have a visit at 24 weeks and then every 6 months afterwards until the final visit or early withdrawal from the study, as long as their Chronocort® dose remains stable. Interim welfare telephone calls and supply of medication (if necessary) will be conducted on a 3-monthly basis (see Section 11.1.8). At Week 24 and then at each 6-monthly visit, the assessments listed below will be conducted. However, if the investigator thinks that the Chronocort® dose needs to be changed at any point after the Week 24 visit, then the subject should undergo an interim dose titration visit or telephone call approximately 4 weeks after the dose has been changed to check on the well-being of the subject. The same assessments as noted for the Week 4 visit will be performed at the interim dose titration visit. If an interim dose titration telephone call is used instead, blood sampling for 17-OHP and A4 and the urine pregnancy test will not be performed but all other Week 4 assessments will be performed.

The subject should then continue with the 6-monthly visit schedule as determined before this visit (i.e. the original timings will be maintained with this extra interim dose itration visit or telephone call added in between).

If the subject has been receiving their Chronocort® medication for the previous 5 days (i.e. sick days rules have not been applied in the preceding 5 days) they will attend the clinic on the morning of the visit. If sick day rules have been applied in the previous 5 days then the visit should be postponed until the subject has been receiving their normal medication for 5 days. Subjects must attend this visit after fasting from 21:00 hours the previous evening.

At each visit, the subject will be asked to return all packs of study medication, including any unused medication, and the number of capsules used and unused will be counted and recorded in the eCRF so compliance can be calculated. The safety pack should also be returned and checked, with any rescue medication use being recorded. Subjects will then be dispensed with new study medication for the next treatment period. If the safety pack has been used then the medication used will be recorded for drug accountability purposes, replaced, and the pack re-sealed and prescribed to the subject for the next study period.

The following assessments will be carried out and recorded at this visit:

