## 11.1.8 Telephone call (within 2 weeks of previous visit)

Following the assessment of the 17-OHP and A4 levels and the clinical evaluation using the adrenal insufficiency checklist conducted at the previous visit, a decision will be made by the investigator whether to adjust the dose for the subject. This assessment must be made within 2 weeks of the visit. All subjects will be contacted by telephone, whether or not a dose adjustment is needed. The subject will receive clear written instructions of the dose they will be taking until the next study visit (even if there is no adjustment to be made) following the telephone call. Subjects will be asked about any AEs at this call and any AEs reported will be recorded in the eCRF.

If a dose titration is needed, an interim dose titration visit or telephone call (at the investigator's discretion) will be required to take place approximately 4 weeks after the decision has been communicated to the participant. The same assessments as noted for the Week 4 visit will be performed at the interim dose titration visit. If an interim dose titration telephone call is used instead, blood sampling for 17-OHP and A4 and the urine pregnancy test will not be performed but all other Week 4 assessments will be performed.

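### SAP 9.3.1 ranks visits by distance to target without giving the scheduled visit precedence, so a post-titration visit can replace an early 6-monthly visit

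*SAP*

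**What the plan says.** SAP 9.3.1 lists vital signs, laboratory data, the endocrine profile and other assessments and ends: "DEXA scans and QoL data will be summarised according to scheduled visit". The same section then sets the rule for competing visits: "If 2 or more visits (including unscheduled visits) occur within the same analysis window, then the visit closest to the target study day" enters the descriptive summaries. For ties: "In case of equidistant visits to the target study day, then the earliest visit will be used in the analyses". The window half-width is "or +/- 3 months (+/- 84 days) for visit 5 and onwards". All visits stay in the listings.

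The protocol creates the competing visits. Under Section 8.1, out-of-range 17-OHP or A4, or symptoms, prompt a dose change. Section 11.1.8 says of the dose decision: "This assessment must be made within 2 weeks of the visit". Section 11.1.7 then asks for an "interim dose titration visit or telephone call approximately 4 weeks after the dose has been changed". If it is a visit, it repeats the Week 4 assessments, including 09:00 and 13:00 hormones. If it is a call, no hormones are taken.

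On the calendar, Protocol Section 8 has visits at 4, 12 and 24 weeks and then states: "Visits thereafter will take place at 6-monthly intervals". Section 11.1 adds: "After Week 18, a visit window of +/- 2 weeks is allowed around each visit". SAP Table 7 counts its targets from first dose instead: Month 12 is day 365, Month 18 is day 548, and so on.

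**The concern.** The two statements in SAP 9.3.1 pull apart. One ties each summary to the scheduled visit; the other lets any visit in the window win on distance. The protocol names interim titration visits separately from unscheduled visits, but a rule for two or more visits covers both.

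The competing visits are not a random sample. An interim titration visit exists only for a subject whose dose was changed, usually because a hormone result was out of range. If it displaces the scheduled visit, the summary loses the result that prompted the change and gains one taken after it. The outputs exposed are the by-visit disease control percentages (SAP 13.2.1) and the SDS and absolute hormone values (SAP 13.2.2). The expected direction is towards better control.

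**Working it through.** **Inputs**

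| Quantity | Value | Source |
|---|---|---|
| d = scheduled day minus target day | −14 to +14 if visits are centred on the targets | Protocol 11.1, SAP Table 7 |
| Visit to dose decision | 0 to 14 days | Protocol 11.1.8 |
| Decision to interim visit | about 28 days | Protocol 11.1.8 |
| g = gap from scheduled to interim visit | 28 to 42 days | sum of the two rows above |
| Window from Visit 5 | ±84 days | SAP 9.3.1 |

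**1. The plan's own windows.** 365 − 84 = 281 and 365 + 84 = 449, as Table 7 states for Visit 5. The same arithmetic (±21 days for Visit 2, ±28 for Visits 3 and 4, ±84 from Visit 5) reproduces every range in the table.

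**2. When the interim visit wins.** It lies at d + g, so it wins if |d + g| < |d|. As g is positive, this means d < −g/2. The scheduled visit must precede the target by more than 14 days (g = 28), 17.5 days (g = 35) or 21 days (g = 42). A visit on or after its target (d ≥ 0) never loses to its own interim visit.

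**3. Visits centred on the Table 7 targets.** There are 29 values of d and 15 of g, so 435 day combinations. None gives a replacement, at Visit 4 or from Visit 5 on. The extreme case (d = −14, g = 28) puts the interim visit at +14, a tie that goes to the scheduled visit. Visits 2 and 3 (±3 days) give 0 of 105 each. If the 4 weeks are read loosely, 4 of 522 combinations replace (g from 25) or 16 of 638 (g from 21).

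**4. Visits counted from Week 24.** With 6 months taken as 182.625 days from day 169:

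| Visit | Nominal day | Table 7 target | Offset |
|---|---|---|---|
| 5 | 352 | 365 | −13 |
| 6 | 534 | 548 | −14 |
| 7 | 717 | 730 | −13 |
| 8 | 900 | 913 | −13 |

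- On-time visit, offset −14, g = 28: interim visit at +14, a tie, so the scheduled visit is kept. Late visits are kept as well.
- Days evenly spread over ±14 around offset −14 (d from −28 to 0): replaced at 14 of 29 days (g = 28), 11 of 29 (g = 35) and 7 of 29 (g = 42). Over all g, 161/435 = 37.0%.
- Offset −13: one day fewer at each of the 15 gaps, (161 − 15)/435 = 146/435 = 33.6%.
- Continuous days, offset −13.5: share = (27.5 − mean g/2)/28. With g from 28 to 42 (mean 35), 10/28 = 35.7%. With the decision at 7–14 days and the interim visit 21–35 days after it (mean 38.5), 8.25/28 = 29.5%.

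The range is therefore about 30–37% of interim visits with blood sampling.

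**5. Illustration for the control rate; all inputs except the 37% are pure assumptions.** Suppose 10–40% of subjects have an interim sampling visit at a given time point, 37% of these displace an uncontrolled result, and 30–60% of the substituted results are in range. The overstatement is 0.10 × 0.37 × 0.30 = 1.1 to 0.40 × 0.37 × 0.60 = 8.9 percentage points. On the step 3 calendar with g of at least 28 days, it is 0.

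**The case against.** The strongest reply is that the swap needs an early visit even on the less favourable calendar. All of the 30–37% comes from visits held before their nominal Week 24-based day. Protocol Appendix 9 (Version 7.0) also explains the ±2-week window: Week 24 falls short of 6 months, and the window lets sites bring visits onto a 6-monthly rhythm. That would move visits later, towards the targets. This stands, and it makes the even spread a scenario rather than an expectation. It does not remove the problem, because neither Section 8 nor Section 11.1.7 requires realignment and an early visit remains within the rules.

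Interim contacts may also be telephone calls without hormone results. This stands too, but only in part: Appendix 9 shows the call option arriving with Version 12.0 (September 2019). Before that, a dose change after Week 24 required a visit.

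Three stronger readings are tempting and are not supported:

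- *The rule routinely removes the out-of-range results that led to titration.* Step 3 gives zero when visits sit within ±14 days of the targets and the interim visit is at least 28 days later.
- *Other unscheduled visits, or visits delayed by COVID-19, produce the same selective swap.* A late visit cannot lose to its own titration visit. Protocol 11.1.12 gives adverse-event follow-up as its example of an unscheduled visit, and Section 8.1 discourages repeat androgen testing at unscheduled dose changes, so many such visits would have no hormone result to substitute.
- *The scheduled visit's safety laboratory data, vital signs and quality-of-life data would be lost as well.* The rule does speak of the visit, and interim visits lack these assessments. But the SAP nowhere says that a visit without an assessment replaces one that has it, and the laboratory shift tables use on-treatment minima and maxima. The wording is ambiguous here; loss is not established.

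**Conclusion.** The point holds as a conditional risk confined to Visit 5 onwards. SAP 9.3.1 contradicts its own scheduled-visit basis, and whenever its rule does replace a scheduled hormone result with a titration follow-up, the selection depends on the outcome and tends to favour control. Given an interim visit at least 28 days later, the size is zero if visits fall within ±14 days of the Table 7 targets, and zero if they are on time or late on the Week 24 calendar. It is about 30–37% of interim visits with sampling if days are evenly spread on that calendar.

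A reader might take that range as the expected frequency, or the 1 to 9 points in step 5 as an estimate of bias. Neither is warranted: the documents give no visit-day distribution, no titration rate and no split between visits and calls. The study schema figures could not be read and might show the intended calendar. The affected outputs are descriptive secondary summaries without formal comparisons. The correction is still worth making, because the rule as written can shift the by-visit control rates and the remedy is small.

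**What to change.** Replace the selection rule in SAP 9.3.1 with:

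> For each parameter, the result from the scheduled visit is used. A result from an interim titration or unscheduled visit in the window is used only if the scheduled visit has no result for that parameter, and is flagged. If two scheduled visits fall in one window, the one closest to target is used.

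The rule must work per parameter. A version that admits other visits only when no scheduled visit falls in the window would discard a valid interim hormone result when the scheduled sample is missing. The SAP should also say whether the 09:00 and 13:00 samples count as separate parameters.

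In addition, reconcile the Table 7 target days with the protocol's 6-monthly visits after Week 24, so that both documents use one calendar.

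Cost: negligible programming work and no new data. With precedence in place, displacement by an interim visit falls to zero by construction wherever the scheduled result exists. Where visits were on target, the summaries do not change.
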